6.6 Sample Size Justification

Sample size selection was based on the feasibility of completing a small number of subjects in a pilot study for safety assessments. A total of 5 patients will be enrolled in this study.

6.7 Statistical Analysis Plan

Data analysis will be conducted using de-identified data in SPSS or SAS statistical software.

Study Population Analysis

The distributions of the following characteristics will be tabulated and presented with descriptive statistics (i.e. mean, standard deviation, median, minimum, maximum, and patient count for continuous variables, and counts with percentages for categorical variables):

- Demographics
- Medical and surgical history
- Final study exit classification (completed, discontinued, withdrew)

Primary Safety Endpoint

The primary safety variable will be complication rates following treatment (XIAFLEX®). Complications – specifically focus on pain, fever, genital lesions, or postoperative AEs related to treatment (XIAFLEX®)

Secondary Efficacy Endpoints

The secondary endpoints will be evaluated with the following tests:

- The percentage of subjects needing further intervention for treatment of urethral stricture during the 2 years follow-up. Further intervention – defined as any medical or surgical intervention for treatment of urethral stricture.
- Incidence of urethral stricture recurrence within 2 years following initial treatment will be calculated and presented with descriptive statistics
- Elapsed time to urethral stricture recurrence and elapsed time to additional intervention for urethral stricture treatment within 2 years following initial treatment will be calculated and presented with descriptive statistics
- Efficacy of XIAFLEX® treatment in improving obstructive voiding dysfunction will be analyzed using paired t-test for the difference in uroflow and post-void residual measurements before and after study treatment (collected at baseline, 6-week post treatment and follow-up visits)
- Quality of life will be analyzed using paired t-test for the difference in AUA scores before and after study initial treatment (collected at baseline, 6-week post treatment and follow-up visits)

Secondary Safety Endpoints

The results of the following safety endpoints will be calculated and presented with descriptive statistics for all patients receiving study treatment.

- Complication rates following treatment – specifically pain, fever, genital lesions, or postoperative complaints secondary to treatment
- Incidence of formation of spongiosclerosis or change in length and extent of spongiosclerosis
- Incidence of change in normal urethra structure proximal to injected tissue
- Incidence and severity of treatment-emergent AEs/SAEs during the study
- Proportion of patients completing study treatment
- Proportion of patients discontinuing due to treatment related complications

7.0 Benefits

This study may not directly benefit participants but may provide information that may accede a larger study that will benefit future clinical practice and patients.

8.0 Risks

The following adverse reactions have been associated with XIAFLEX® in treatment of Peyronie's disease:

- Penile hematoma (includes injection site hematoma and penile hematoma)

- Penile swelling (includes injection site swelling, penile edema, penile swelling, local swelling, scrotal swelling, and injection site edema)
- Penile pain (includes injection site pain, penile pain, and injection site discomfort)
- Penile ecchymoses (includes contusion, ecchymoses, penile hemorrhage, and injection site hemorrhage)
- Blood blister
- Penile blister
- Pruritus genital
- Painful erection
- Erectile dysfunction
- Skin discoloration
- Procedural pain
- Injection site vesicles
- Localized edema
- Dyspareunia
- Injection site pruritus
- Nodule
- Suprapubic pain
- Corporal rupture (penile fracture)
- Penile “popping” sounds or sensations

These adverse reactions were reported in XIAFLEX® clinical trials in patients with Peyronie’s disease, from which most adverse reactions were reported as local events of the penis and groin and the majority of these events were of mild or moderate severity, and most (79%) resolved within 14 days of injection. The adverse reaction profile was similar after each injection, regardless of the number of injections administered ¹⁰.

Risks related to lidocaine injections include, but are not limited to:

- Hypotension
- Edema
- Redness at injection site
- Small red or purple spots on skin
- Skin irritation
- Constipation
- Nausea
- Vomiting
- Confusion
- Tremors
- Dizziness
- Headache
- Numbness and tingling
- Drowsiness
- Severe allergic reactions
- Dark urine
- Sudden feeling of warmth with muscle stiffness and pain
- Feeling hot or cold

- Anxiety

Other risks related to the injections include, but are not limited to:

- Bleeding
- Infection
- Fistula
- New stricture or scar tissue
- Inefficacy
- Incontinence
- Need for surgical intervention
- Lymphadenopathy
- Lymph Node Pain
- Inguinal Pain
- Need for suprapubic tube
- Need for extensive reconstruction in the future
- Fistula (urethrocutaneous)
- Periurethral abscess
- Urethral diverticulum
- Acute urinary retention
- Need for urethral catheterization

Risk related to breach of confidentiality

The risks of participants in this project involve the use of PHI for the initial access to study-related data. Anytime such data is accessed and stored by handlers outside the domain of clinical routine, the risk of breached data security is increased, however all means necessary have been inputted to secure the information. Medical record numbers and patient names will be used to access the patient's medical record. Once the data collection is complete, the medical record numbers, patient names, and any other PHI will be destroyed.

Risks related to completing the surveys

The cognitive assessments ask about disease and health. Thinking about these things may make the patient uncomfortable. The patient may also feel a loss of privacy by answering the questions. The responses will be kept confidential and the patient may skip any questions he does not want to answer.

9.0 Safety Monitoring

A Data and Safety Monitoring Board (DSMB) will be established to monitor adverse reactions and the safety of the study. The DSMB will consist of experts in the relevant biomedical fields of urology and biostatistics. The members will have no direct relationship to the study (will not involve in any study related activities but may have their inputs in the study design and changes). The DSMB will review the protocol of the study and periodically monitor the progress, data, outcomes and safety during the study. An analysis will be performed after 5 patients have completed their study treatment and 6-week post treatment visits. All adverse events and reactions will be tabulated and presented to the DSMB. Further safety analysis will be performed by the biostatistician on the DSMB as necessary.

9.1 Adverse Events

Adverse events (AE) will be monitored and collected by the study team from the point of signed consent to the end of patient's participation in the study. For each AE, a detailed explanation will be obtained from the patient and patient's medical record. All AEs are to be recorded on the case report forms located in the patient's study binder and master database maintained by the principal investigator.

Definition of Adverse Events

An adverse event (AE) is defined as any untoward medical occurrence associated with the use of a drug in humans, whether or not considered drug-related. All adverse events, including observed or volunteered problems, complaints, or symptoms, are to be recorded. Subjects will be instructed to report any adverse event they experience to the investigator/study staff.

Investigators will assess for adverse events at each visit and record accordingly. Any medical condition that is present when a subject is screened or present at baseline that does not worsen or deteriorate will not be reported as an adverse event. However, medical conditions present at baseline that change in severity at any time during the study will be reported as an adverse event. The investigator will exercise his medical and scientific judgment in deciding whether an abnormal assessment is clinically significant. The investigator will rate the severity of and clarify each adverse event based on the definitions below.

Assess of Severity of Adverse Event:

- Mild – transient in nature and generally does not interfere with normal activities
- Moderate – sufficiently discomforting to interfere with normal activities
- Severe – incapacitating, causing inability to perform normal activities

Assessment of Adverse Event and Study Drug Relatedness:

No related – definitely not related to study drug and is judged clearly due to causes other than study drug

Unlikely related – follows a temporal sequence from study drug administration, such that a relationship is not likely and could be reasonably explained by the subject's current medical condition or other standard of care treatment the subject is receiving

Possibly related – follows a temporal sequence from study drug administration, but may be due to another cause and could also be reasonable explained by the subject's current medical condition or other standard of care treatment the subject is receiving

Definitely related – clearly related to study drug administration

9.2 Serious Adverse Events

An adverse event is considered serious if it results in any of the following:

- Death
- Life-threatening adverse event – subject is at immediate risk of death due to adverse event occurrence
- Requires inpatient hospitalization or prolongs existing hospitalization
- Results in persistent or significant disability/incapacity
- Significant medical event that may require medical/surgical intervention to prevent one of the outcomes above

9.3 Unanticipated Adverse Events

The following are examples of adverse events considered to be unanticipated adverse events that must be reported to the USF Institutional Review Board (IRB) promptly, or within five (5) calendar days:

- A single occurrence of a serious, unexpected event that is uncommon and strongly associated with drug exposure (such as angioedema, agranulocytosis, hepatic injury, or Stevens-Johnson syndrome);
- A single occurrence, or more often a small number of occurrences, of a serious, unexpected event that is not commonly associated with drug exposure, but uncommon in the study population (e.g., tendon rupture, progressive multifocal leukoencephalopathy);
- Multiple occurrences of an AE that, based on aggregate analysis, is determined to be an unanticipated problem. There should be a determination that the series of AEs represents a signal that the AEs were not just isolated occurrences and involve risk to human subjects;
- An AE that is described or addressed in the investigator's brochure, protocol, or informed consent documents, but occurs at a frequency or severity that is inconsistent with prior observations.
- A serious AE that is described or addressed in the investigator's brochure, protocol, or informed consent documents, but for which the rate of occurrence in the study represents a clinically significant increase in the expected rate of occurrence (ordinarily, reporting would only be triggered if there were a credible baseline rate for comparison).
- Any other AE or safety finding that would cause the sponsor to modify the investigator's brochure, study protocol, or informed consent documents, or would prompt other action by the IRB to ensure the protection of human subjects.
- Any breaches in confidentiality that would place the participant or others at risk;
- Any change in FDA labeling or withdrawal from marketing of a drug, device, or biologic used in a research protocol;
- Any change to the protocol that was taken without prior IRB approval to eliminate apparent immediate hazard to a research participant;
- Incarceration of a participant when enrolled on a study not approved under Subpart C provisions; or
- Breach of privacy or confidentiality including the loss of data on a computer or any electronic device which holds private or confidential information.

A comprehensive list of all adverse and serious adverse events will be submitted with each continuing review application to the USF IRB.

9.4 Study Stopping Criteria

Study termination may be recommended for any perceived safety concern based on clinical judgment, including by not limited to a higher than anticipated rate of $\geq 1\%$ for any component resulting in an unanticipated SAEs. Subjects will also be withdrawn from the study if benefits are outweighed by the risks.

The study will be stopped altogether if there is one case of study treatment adversely affecting other post treatment intervention and/or urethroplasty in patients with recurrence of urethral stricture as determined by the principal investigator and DSMB to be related to study treatment.

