2.3 Rationale for Urethral Stricture Treatment with XIAFLEX®

Urethral strictures, like Dupuytren's contractures and Peyronie's disease, are associated with a total increase in type I and type III collagen smooth muscle¹⁰. A recent study investigated injecting urethral strictures with high dose CHC in rats showed reduction in urethral fibrosis as well as a reduction in collagen type I and III expression in the rodents' urethral strictures¹¹. We wish to investigate if CHC would have a similar impact on urethral strictures in men when administered in a similar fashion to the Peyronie's disease algorithm.

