6.5.3 Post-treatment (Days 2 or 3)

The patient will be instructed to return to clinic within 2-3 days of the injection

- Perform physical exam
- Perform uroflow, post-void residual (PVR) measurements
- Administer AUA questionnaire
- Evaluate and record concomitant medications
- Assess for adverse events

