6.5.7 Early Termination

Early Discontinuation

Reasons for discontinuation of treatment may include, but are not limited to, the following:

- Patient withdrawal of consent
- Any medical condition that the Investigator determines may jeopardize the patient's safety if he continues in the study
- Investigator determines it is in the best interest of the patient
- Patient noncompliance, such as missing scheduled visits, non-adherence with concomitant medications, etc.
- Lost to follow-up
- If patients have no clinical response to the intervention and have persistent clinical manifestations of their stricture disease they may elect to undergo definitive management in

the form of urethral dilation, urethrectomy, or urethral reconstruction. They will still be followed per above protocol and included in all statistical analysis.

After study treatment is discontinued, patient will be asked to remain in the study whenever possible and complete all study visits according to the planned schedule of assessments (except for patients who have withdrawn consent and are lost to follow-up). The primary reason for premature discontinuation of study treatment should be documented appropriately. If a patient chooses to discontinue study treatment and withdraw from the study, then the patient will be asked to return to the clinic for the early termination (ET) visit and complete all assessments.

Patients who prematurely discontinue study treatment will not be replaced.

Early Withdrawal

All patients have the right to withdraw from study participation without prejudice at any time during the study. If a patient terminates participation in the study, the Investigator will make a reasonable effort to determine the cause of study withdrawal. If, for whatever reason, a patient withdraws from the study or the study is terminated while the patient is receiving study treatment, an early termination (ET) visit will be performed.

Patients who prematurely withdraw from the study will not be replaced.

The following procedures will be performed at the ET visit if allowed by patient:

- Perform physical exam
- Perform cystoscopy, urethra ultrasound, uroflow, PVR measurements, and evaluate length and extent of spongiosclerosis
- Administer AUA questionnaire
- Evaluate and record concomitant medications, medical and surgical history
- Assess for adverse events

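### With 5 patients, the 1% figure in section 9.4 is met by any single unanticipated SAE, and nothing holds the next patient's injection while that event is reviewed

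*Combined protocol and SAP*

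**What the plan says.** Section 9.4 has two parts. The first is discretionary: termination can be recommended for any safety concern on clinical judgment, and one named ground is "a higher than anticipated rate of $\geq 1\%$ for any component resulting in an unanticipated SAEs". The protocol prints no anticipated rate and does not define what a component is. The second is mandatory but narrow: the study stops after one case in which treatment harms a later intervention or urethroplasty, once the principal investigator and DSMB judge it related.

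On size, section 6.6 states "A total of 5 patients will be enrolled in this study" and gives feasibility as the reason. Section 6.5.7 adds "Patients who prematurely withdraw from the study will not be replaced", and says the same of patients who discontinue treatment. The schedule in section 13.0 shows one treatment visit per patient.

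On review, section 9.0 has the DSMB "periodically monitor the progress, data, outcomes and safety during the study", with no interval given. It sets one analysis by time point: "An analysis will be performed after 5 patients have completed their study treatment and 6-week post treatment visits". Section 9.3 requires unanticipated events to reach the IRB within five calendar days.

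**The concern.** A threshold of 1% suggests that a rate will be estimated and compared with a limit. Five patients cannot yield a non-zero rate anywhere near 1%, so the figure cannot separate an acceptable result from an unacceptable one.

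The larger question is what happens after the event. Safety is the primary objective. The stricture-injection data that the protocol describes come from rats (sections 2.3 and 5.2), and section 2.3 says "We wish to investigate if CHC would have a similar impact on urethral strictures in men". Each patient is injected once, so reviewing an event can protect only those not yet injected. At the DSMB's one timed analysis that number is zero. Before then, the next patient could be injected within the IRB reporting window, or ahead of the next undated DSMB review, without any departure from the protocol.

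**Working it through.** **Inputs.** From the protocol: n = 5 (6.6), no replacement (6.5.7), one treatment day per patient (6.5.2, 13.0), threshold 1% (9.4). There is no calculation to reproduce: 5 rests on feasibility, and the 1% has no derivation.

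**Step 1: smallest non-zero rate.** One event among n treated patients is a rate of 1/n: 100, 50, 33.3, 25 and 20% for n = 1 to 5. Each exceeds 1%. One event would first fall below 1% at n = 101.

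**Step 2: the other reading.** If the clause means at least one percentage point above an anticipated rate, one event in 5 meets it unless that rate exceeds 20 − 1 = 19%. With fewer patients treated, the limit is higher still.

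**Step 3: what acts on the next injection.**

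- 9.4, discretionary ground: permits a recommendation to terminate; requires no pause.
- 9.4, mandatory rule: stops the study, but only for harm to a later intervention or urethroplasty.
- 9.3: IRB report within five calendar days; no effect on dosing.
- 9.0: DSMB review without dates, further safety analysis as needed, and one timed analysis after all 5 are treated.
- 6.5.2 and 6.5.7: observation and discontinuation of the patient already treated.
- 6.5: patients go from consent to treatment, with no interval between patients stated.
- 10.0: regular data monitoring by the principal investigator and coordinator; no link to dosing.

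None suspends the next injection while an event is reviewed. Early detection is plausible, since section 6.5.3 says "The patient will be instructed to return to clinic within 2-3 days of the injection", but that helps only if injections are spaced.

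**Step 4: whom a hold could reach.** Let p be the true per-patient chance of an event that invokes the hold, with patients independent. The documents give no p; 1, 5, 10 and 20% are assumptions, as are both timing scenarios.

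- Any event in 5: 1 − (1 − p)^5.
- Scenario A, event known before the next injection. Someone left uninjected: 1 − (1 − p)^4. Mean number left: sum over k = 1 to 4 of p(1 − p)^(k−1)(5 − k).
- Scenario B, one more patient injected first. Someone left: 1 − (1 − p)^3. Mean number left: sum over k = 1 to 3 of p(1 − p)^(k−1)(4 − k).

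The rows marked as given an event divide by the first row.

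| | p = 1% | 5% | 10% | 20% |
|---|---|---|---|---|
| Any event in 5 | 4.9% | 22.6% | 41.0% | 67.2% |
| A: someone left uninjected | 3.9% | 18.5% | 34.4% | 59.0% |
| A: same, given an event | 80% | 82% | 84% | 88% |
| A: mean number left | 0.099 | 0.476 | 0.905 | 1.638 |
| A: mean number left, given an event | 2.0 | 2.1 | 2.2 | 2.4 |
| B: someone left uninjected | 3.0% | 14.3% | 27.1% | 48.8% |
| B: same, given an event | 61% | 63% | 66% | 73% |
| B: mean number left, given an event | 1.2 | 1.3 | 1.4 | 1.6 |

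Worked example, scenario A at p = 10%: 1 − 0.9^4 = 0.3439; 1 − 0.9^5 = 0.4095; ratio 0.840. Mean left: 0.4 + 0.27 + 0.162 + 0.0729 = 0.905; divided by 0.4095, 2.2.

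**Step 5: ceiling on harm avoided.** Patients left uninjected are not harms avoided. If every hold became a stop, the expected further events avoided per trial in scenario A would be the mean number left times p: 0.099 × 0.01 = 0.001; 0.476 × 0.05 = 0.024; 0.905 × 0.10 = 0.09; 1.638 × 0.20 = 0.33.

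**The case against.** The strongest reply is that nothing prevents a pause. The clinical-judgment clause covers any concern, the DSMB can ask for further analysis, subjects are withdrawn if risks outweigh benefits, and this is a single-centre study of 5 patients. DSMB operating procedures are not in the documents and may deal with this. All of that stands. A reader might infer that the trial cannot be halted after an SAE, and the documents do not support that: the power exists, but no written step requires its use before the next injection.

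A reader might also infer that the 1% is an error that makes the trial stop too readily. It does not, because the ground is discretionary and one event already suffices under the clinical-judgment wording. Nor can one say that no anticipated rate exists; one may sit in the investigator's brochure or package insert.

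It is also fair to say that the benefit is modest and uncertain. It depends on assumed rates and on an enrolment pace that the protocol does not give, and a hold that ends in a decision to continue spares nobody. Section 5.2 also reports no urethral or voiding complication in the rat model. Against that, section 2.2.1 reports hemorrhage, edema and necrosis at all dose levels in dogs injected at penile sites including the urethra.

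Finally, a hold limited to event types missing from the risk list would be too narrow. Section 9.3 also treats as unanticipated a listed event of unusual frequency or severity, and section 8.0 lists the local harms that matter most here, such as fistula, periurethral abscess and acute retention.

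**Conclusion.** The point holds in two parts of unequal weight. The 1% figure does no work: one unanticipated SAE is at least 20%, or meets the clause for any anticipated rate up to 19% on the other reading. This needs no assumption beyond the planned size, and correcting it alone changes no trigger and spares no patient.

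The substantive gap is the absence of a written hold. In a pilot whose primary objective is safety, the next patient may be injected after an unanticipated SAE and before anyone independent has reviewed it. How much a hold would protect rests on assumptions. Given an event, someone remains uninjected in 80 to 88% of cases with sequential injection and prompt knowledge, in 61 to 73% if one more patient is injected first, and in none if all 5 are injected before the event is known. Expected further events avoided are at most about 0.001 to 0.33 per trial in the sequential scenario. The change should be made because it is cheap and fits the primary objective; its absence does not invalidate the design.

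**What to change.** In section 9.4, replace the phrase containing the 1% rate with: *any one SAE that is unanticipated as defined in section 9.3, including an event listed in section 8.0 that occurs with a severity or frequency inconsistent with prior observations*.

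Then add: *After such an event, unless it is rated not related to study drug, no further patient is injected until the DSMB has reviewed it and recommended continuing or stopping.*

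The exemption uses the lowest relatedness category in section 9.1, described there as "definitely not related to study drug and is judged clearly due to causes other than study drug"; events rated unlikely related still invoke the hold. Keep the clinical-judgment clause and the one-case rule as they are.

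The cost is one phrase and one sentence, using the DSMB already planned and no extra patients. The downside is a possible enrolment delay of unknown length, since no DSMB turnaround time is stated. With sequential injection, the chance that such a hold leaves someone waiting is about 4% if the true rate is 1% and about 34% if it is 10%. A waiting patient whose screening ultrasound becomes more than 30 days old would need it repeated on the treatment day under section 5.4.
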